8.0 STATISTICAL ANALYSIS

This study is not designed to detect or estimate accurately the true pre-post changes in secondary outcomes related to visual function and macular cysts. Therefore, no formal statistical hypothesis tests will be performed. Analyses will be primarily descriptive and by per participant.

8.1 Analysis

All reported adverse events will be tabulated and presented by system organ class, severity and relationship to study therapy.

Secondary outcomes will be presented for each participant and tabulated over time, as described in Section 7.2. Additionally, these outcomes will compare the changes within the study eye from baseline and the changes between the study eye and control eye over time.

8.2 Sample Size

No formal sample size calculation has been performed as this is a Phase I/II pilot study to evaluate safety. Up to five eyes in each disease group will be evaluated for safety and toxicity following IFN gamma-1b administered topically.

9.0 HUMAN SUBJECTS PROTECTION

9.1 Equitability

Accrual for this study will be equitable among participants meeting the enrollment criteria. Participants of any ethnic background, gender, sexual orientation, or health status will be included according to the inclusion and exclusion criteria previously listed.

9.1.1 Justification for Exclusion of Children Below 12 Years of Age

Children below 12 years of age will be excluded from the study due to limited experience with the treatment in that group of pediatric age patients.

9.1.2 Justification for Inclusion of Children Ages 12 and Above

Children ages 12 and above are eligible for this study as the age of symptom onset for RCD and ESCS is frequently late childhood to early teenage years and there are many affected teenagers. Individuals who are affected earlier tend to have the most severe disease presentation and are the most likely to enroll in future clinical trials. It is anticipated that many children ages 12 and above will be able to comply with the extensive examinations required for this study; however, those who are unable to do so will be excluded.

9.1.3 Safeguards for Vulnerable Populations

The standard in the community is for retinal specialists and general ophthalmologists to provide care and perform procedures for children with RCD and ESCS. [name] and [name] are fellowship-trained pediatric ophthalmologists and the clinic is designed to accommodate children. All of the investigators on this protocol have experience working with children. A pediatrician will be available for consultation if necessary.

9.1.4 Consideration of Persons Who Cannot Consent

Adults unable to understand and sign an informed consent are not excluded from this study unless they are unable to cooperate with evaluation and testing that will be done under this protocol. Experience at the NEI clinic suggests that few, if any, such participants who cannot consent will be able to comply with the extensive examinations required for this study, given that sedation will not be used. In the event that such persons are considered for enrollment, consultation to assess whether an individual has the capacity to provide consent or is able to assign a surrogate, as well as the appropriateness of a surrogate, will be obtained by contacting the NIH Ability to Consent Assessment Team (ACAT) [contact] or [contact]), which is a group trained to conduct these assessments and includes members from Psychiatry, Bioethics and other disciplines.

9.1.5 Justification for Exclusion of Pregnant or Lactating Women

Pregnant women are excluded because the teratogenicity of IFN gamma-1b on a fetus is unknown. Lactating women will also be excluded as it is not known whether or not IFN gamma-1b is excreted in breast milk.

10.0 ANTICIPATED BENEFIT

Participants receiving IP may benefit directly from this study if topical IFN gamma-1b improves visual function. This may include an improvement in visual acuity, visual field, or color vision. Any improvements are expected to persist through the study duration. It is unknown whether participants will maintain any improvements beyond the duration of the trial. The study will also lead to generalizable knowledge that will enhance the investigators' understanding of the use of IFN gamma-1b in macular cystic disease in RCD or ESCS.

11.0 CLASSIFICATION OF RISK

Risk is classified as more than minimal risk for participants receiving IP. For minor children receiving IP, risk is classified as research involving greater than minimal risk, but presenting the prospect of direct benefit to the individual subjects (45CFR 46.405). The risks of this study are reasonable given that the participants suffer significant visual disruption due to macular cystic changes associated with RCD or ESCS. For adults unable to consent, risk is classified as research involving greater than minimal risk but presenting the prospect of direct benefit to the individual subjects.

12.0 CONSENT DOCUMENTS AND PROCESS

Study investigators with consenting privileges will obtain informed consent. All study investigators obtaining informed consent have completed the NIMH HSPU “Elements of Successful Informed Consent” training. Assent will be obtained from minor participants. All participants will receive a verbal explanation in terms suited to their comprehension of the purposes, procedures and potential risks of the study. Participants must have the ability to understand and sign an informed consent form, which must be signed prior to enrollment. Participants will have the opportunity to carefully review the consent and ask questions regarding this study prior to signing and they will be informed that they may withdraw from the study at any time without prejudice to themselves.

If a participant requires the consent to be in larger font in order to read it well, this will be provided. If a participant is visually impaired to the point of being unable to read the consent, s/he can take the consent back with them to read it over with a family member or with the use of magnifying devices. If a participant chooses, the investigator can also read the consent verbatim to the participant and answer any questions that may arise.

The investigator obtaining consent will document the consent process in the participant’s medical record. A signed copy of the informed consent form will be provided to the participant to take home.

12.1 Non-English Speaking Participants

If a non-English speaking participant is unexpectedly eligible for enrollment, the participant will be provided with the CC Short Written Consent Form for Non-English Speaking Research Subjects in the participant’s native language and a verbal explanation of the purpose, procedures and risks of the study. The IRB-approved English consent form will serve as basis for the verbal explanation of the study. The investigator will obtain an interpreter unless the investigator is fluent in the prospective participant’s language. Preferably, the interpreter will be someone who is independent of the participant (i.e., not a family member). Attempts to locate independent interpreters will be made through the Clinical Center. The interpreters will translate the IRB-approved English consent form verbatim and facilitate discussion between the participant and investigator.

The IRB-approved English consent form will be signed by the investigator obtaining consent and a witness to the oral presentation. The CC Short Written Consent Form will be signed by the participant and a witness who observed the presentation of information. The interpreter may sign the consent document as the witness and, in this case, will note “Interpreter” under the signature line. A copy of both signed forms will be provided to the participant to take home.

The investigator obtaining consent will document the consent process in the participant’s medical record, including the name of the interpreter. Further, all instances of use of the CC Short Written Consent Form will be reported to the IRB at the time of annual review. If the CC Short Written Consent Form is used three times or more for the same language within an IRB approval period, this will be reported to the IRB immediately.

Interpreters will also be present for other protocol procedures as necessary.

13.0 DATA AND SAFETY MONITORING

The NEI Serious Adverse Event (SAE) Review Committee is responsible for monitoring data and safety and will exercise oversight of the clinical investigation independently from the study investigators.

13.1 Coordinating Center

The Emmes Corporation (Emmes) has been assigned as the Coordinating Center for this trial to conduct data collection, protocol monitoring, data analysis and reporting. The Coordinating Center provides routine monitoring of study participants’ data. Monitoring visits will occur on a schedule depending on the status of the study. More frequent monitoring visits will be performed at the beginning of the study when enrollment is open. Monitoring will decrease as enrollment closes and as participant follow-up continues.

Although Emmes advises the NEI Clinical Director (CD) and Principal Investigator on data and statistical activities, the Coordinating Center staff does not have direct access to or interaction with participants.

13.2 NEI Serious Adverse Event Review Committee

The NEI Serious Adverse Event Review Committee, which consists of the NEI Clinical Director and three other NEI physicians, will be responsible for reviewing any reported serious safety events, if they occur under this protocol. The Committee will review accumulating data on a semiannual basis to determine whether the study should continue. If changes to the protocol are indicated, recommendations will be made to the NEI Director and IRB who will consider and act on such recommendations in a timely manner. Should any serious suspected adverse reactions occur, the NEI Clinical Director may, at his discretion, assemble the Review Committee before the scheduled date to consider whether the study should move forward. The Review Committee or Principal Investigator can stop the study at any time if it appears there are any unexpected serious suspected adverse reactions that would outweigh any potential benefits of treatment. In addition, if three or more participants experience non-serious suspected adverse reactions that require temporary or permanent cessation of the investigational product, the Principal Investigator shall report this to the NEI Clinical Director. The NEI Clinical Director may convene the Review Committee before the scheduled time to consider the cessation of the study as a whole. The NEI Serious Adverse Event Review Committee or IRB may recommend temporarily suspending or closing enrollment, or stopping the study at any time due to safety concerns, demonstration of efficacy or lack of efficacy or slow recruitment.

13.3 Criteria for Stopping the Study

The NEI SAE Review Committee may recommend temporarily suspending or closing enrollment, or stopping the study at any time due to safety concerns. Enrollment will be temporarily suspended if a participant experiences a suspected serious adverse reaction. The NEI SAE Review Committee will review the event and determine whether enrollment may be restarted. Enrollment will be permanently suspended if two or more participants experience serious adverse reactions assessed as related to the investigational product itself. Irrespective of study status, participants who are already enrolled will be followed up for the previously delineated time period.

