15.0 REPORTING OF UNANTICIPATED PROBLEMS, PROTOCOL DEVIATIONS AND ADVERSE EVENTS

The Principal Investigator is responsible for detecting, documenting, and reporting unanticipated problems, adverse events (AEs), including serious adverse events (SAEs), and deviations in accordance with NIH policy, IRB requirements, and federal regulations. Relatedness to the research of all serious adverse events will be determined by the PI in consultation with the Clinical Director (CD).

Serious unanticipated problems, serious adverse events (including deaths) that are not unanticipated problems and serious protocol deviations will be reported to the IRB and CD as soon as possible and in writing not more than 7 days after the PI first learns of the event, unless immediate reporting is waived for specific serious adverse events as noted below. Not serious unanticipated problems and not serious deviations will be reported to the IRB and CD as soon as possible and in writing not more than 14 days after the PI first learns of the event. Written reports will be submitted in PTMS.

All adverse events, deviations, and unanticipated problems will be summarized and reported at the time of Continuing Review.

The PI will immediately report SAEs to the Sponsor according to the requirements of 21 CFR 312.64(b). The PI will record non-serious AEs and report them to the Sponsor as soon as possible.

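### The two mandatory criteria in 13.3 suspend enrollment but do not hold drops for participants mid-course, and no timed decision on dosing is required

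*Combined protocol and SAP*

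**What the plan says.** Section 13.3 has two criteria written as obligations.

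- First: "Enrollment will be temporarily suspended if a participant experiences a suspected serious adverse reaction". The step that follows is "The NEI SAE Review Committee will review the event and determine whether enrollment may be restarted".
- Second: "Enrollment will be permanently suspended if two or more participants experience serious adverse reactions assessed as related to the investigational product itself".

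The section closes with "Irrespective of study status, participants who are already enrolled will be followed up for the previously delineated time period", which concerns follow-up visits and is silent on drops.

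Section 13.2 schedules committee review twice a year and makes the committee responsible for reviewing reported serious safety events. It adds: "Should any serious suspected adverse reactions occur, the NEI Clinical Director may, at his discretion, assemble the Review Committee before the scheduled date". It also gives a power to stop: "The Review Committee or Principal Investigator can stop the study at any time if it appears there are any unexpected serious suspected adverse reactions", where these would outweigh the potential benefit. Under 13.2 the committee or the IRB may recommend stopping at any time, and 13.3 repeats this for the committee.

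Under 15.0, serious events are "reported to the IRB and CD as soon as possible and in writing not more than 7 days" after the investigator learns of them, and "Relatedness to the research of all serious adverse events will be determined by the PI in consultation with the Clinical Director".

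Where the protocol does say what happens to the drops (ocular redness in 4.4, pregnancy in 6.2), it speaks of the affected participant only. Section 6.1 likewise lets investigators withdraw the participant who had the reaction.

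**The concern.** A section on stopping criteria would be expected to say what happens to people currently receiving the product. Here the required action protects future participants only. Someone already sent home with drops continues unless a person decides otherwise.

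Three features of the trial make this matter. Participants dose themselves at home, and the flowsheet shows the Week 1 telephone call as the only scheduled contact between Day 3 and Week 2. No minimum interval between participants is set within a stage, so courses can overlap. The only prior human results that section 1.0 reports are from five participants given 10 to 30 µg in a single session, whereas this trial gives 112 µg a day for about two weeks, from age 12. The pause after the first four participants reach Week 8 also acts on enrollment only.

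**Working it through.** The protocol states no figure to reproduce. The textual finding comes from setting the clauses side by side.

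| Provision | Acts on | Force | Deadline |
|---|---|---|---|
| 13.3, first criterion | enrollment | mandatory | none for the review |
| 13.3, second criterion | enrollment | mandatory | none |
| 13.2, early meeting | whole study | discretionary | none |
| 13.2, investigator or committee stop | whole study | discretionary | none |
| 13.2 and 13.3, recommendation to stop | whole study | discretionary | none |
| 4.4, 6.1, 6.2 | affected participant | mixed | none |

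No row obliges anyone to decide whether other participants keep dosing.

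**Inputs for the size.** Under 4.5.3 drops run from Day 1 to the day before the Week 2 visit (Day 14 ± 5), so a course lasts 13 days, with a range of 8 to 18. Section 4.4 describes two weeks, so 14 days is also shown. The daily dose is 16 drops × 7 µg = 112 µg. Ten participants enroll, in stages of 4 and 6, and 4.2 expects recruitment within 12 months.

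**Assumptions.** Start dates are uniform over the enrollment period and the event is uniform within the affected participant's own course. The staged version places 4 starts over days 0 to 124, a 56-day halt, and 6 starts over days 180 to 365.

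**Chance that another participant is on drops, given an on-course event** (simulation, 400,000 runs):

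| Enrollment | 8-day course | 13-day | 14-day | 18-day |
|---|---|---|---|---|
| 10 over 365 days | 0.179 | 0.275 | 0.292 | 0.360 |
| Staged, 4 then 6 | 0.188 | 0.289 | 0.308 | 0.377 |

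Closed-form check for 13 days: 1 − (1 − 13/365)^9 = 0.278. By stage, for 13 and 14 days, the values are 0.273 and 0.290 (4 over 124 days) and 0.298 and 0.317 (6 over 185 days). The planned pace therefore gives about 0.27 to 0.32. If a stage filled in 56 days, which 4.2 does not expect, the 13-day values would be 0.509 (stage of 4) and 0.689 (stage of 6).

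**Whole-trial chance of at least one such overlap** (13-day course, assumed rate p of an on-course serious reaction per participant):

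| p | Any event, 1 − (1 − p)^10 | Overlap, even | Overlap, staged |
|---|---|---|---|
| 1% | 0.096 | 0.027 | 0.029 |
| 2% | 0.183 | 0.053 | 0.055 |
| 5% | 0.401 | 0.129 | 0.134 |
| 10% | 0.651 | 0.240 | 0.251 |

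**Events after enrollment is complete.** A share of 0.117 (even) or 0.121 (staged) of on-course events fall after the last participant has started, when neither criterion changes anything.

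**Exposure at stake.** Let R, the days left for an overlapping participant, be uniform on 0 to 13.

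- Mean days left: 13/2 = 6.5 days, or 6.5 × 16 = 104 drops, or 104 × 7 = 728 µg.
- Spared by a call at 24 hours with no resumption: E[(R − 1)+] = 72/13 = 5.54 days, about 89 drops or 620 µg.
- Spared by a call at 24 hours with resumption on day 7: 54/13 = 4.15 days.

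**Cost of an immediate 7-day hold.**

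- Dosing days removed: E[min(R, 7)] = 66.5/13 = 5.12.
- Share whose course ends during the hold: 7/13 = 54%.
- Share with fewer than five days dosed when the hold starts: 5/13 = 38%. If dosing resumes after 7 days, each of these finishes with 13 − 7 = 6 days.

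**The case against.** The strongest reply is that this is a single-center pilot of about ten people with authority close at hand. The investigator can stop the study without a committee. The Clinical Director sits on the committee, is told of serious events as soon as possible and is consulted on relatedness. The sponsor is told of serious events immediately under 15.0, and unscheduled safety visits are allowed under 4.4. Whether to hold automatically or by judgement is a legitimate design choice, and the expected gain is small: at an assumed 5% rate it is about 10 × 0.05 × 9 × 13/365 × 5.54 = 0.9 participant-days for the whole trial. A hold triggered by a merely suspected reaction also shortens courses in a very small study.

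Much of this stands. It limits the size and shows the gap is not one of authority or awareness. It does not supply the missing obligation: every route to stopping other participants' drops remains discretionary.

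Two stronger readings are tempting. A reader might infer that the second criterion carries no review, because its sentence names none. That does not follow: a related serious reaction is also a suspected one, so the event review in 13.3 and the committee's general duty in 13.2 reach each of them. A reader might also infer that the review would wait for the semiannual meeting. The text sets no date, but it orders a review of the event and allows an early meeting, so a long wait is only a worst case.

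**Conclusion.** The concern holds as a gap in the rule. Meeting either mandatory criterion suspends enrollment, leaves other participants' drops untouched, and has no effect once enrollment is complete. Review is required, but it is undated and need not address dosing. The documents do not support calling this a contradiction, an absence of review or a lack of power to stop. Nor does the last sentence of 13.3 tell anyone to keep dosing, since it settles follow-up only.

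The size is modest: about 0.27 to 0.32 for an overlap given an on-course event, and about 3% to 24% for the whole trial at assumed rates of 1% to 10%. These figures rest on uniform start dates over 12 months, uniform event timing and a 13- or 14-day course. The event rates are assumptions, because the protocol gives none. Appendix 2, part of section 5 and the operating procedures were not in the text available for this review and should be checked for a dosing instruction. The change is worth making because it is cheap and safety is the primary outcome.

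**What to change.** (1) In 13.3, after the two-reaction sentence, add:

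> When either criterion is met, investigational product is held for all participants still on drops, and study staff will telephone each of them within 24 hours. If any participant is on drops or enrollment is open, the NEI SAE Review Committee will meet within 7 days and record whether dosing may resume and, for the first criterion only, whether enrollment may restart. Held doses are not made up and visits keep their dates.

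(2) In 13.2, change the Clinical Director's discretion over an early meeting to: *will assemble the Review Committee as stated in 13.3, and may otherwise do so before the scheduled date*.

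This is a cheap improvement: two wording changes and, at most, one extra meeting of an existing four-physician committee per event. No meeting is forced when nobody is on drops and enrollment is closed.

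The downside is lost treatment. An immediate 7-day hold removes about 5.1 dosing days on average and ends the course for about 54% of those held, which weakens their descriptive efficacy data. About 38% of those held would finish with fewer than five days of treatment, but only if dosing does not resume. The replacement rule in 3.0 (up to two extra participants) applies only if such a participant withdraws.

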14.0 QUALITY ASSURANCE

The NEI and Emmes maintain quality control by adhering to standard operating procedures (NEI QA program and NEIS standard operating procedures). These procedures cover the full protocol cycle beginning with staff credentialing and training, and protocol development and approval, through database development, data collection, monitoring and analysis, and finally manuscript preparation at the conclusion of the study. Data quality assurance is of the utmost importance to the NEI and Emmes. The two groups use a quality assurance system that relies on real-time data checks and reports throughout the course of a study to ensure the accuracy of information. This system is a secure and confidential data management system that stores data and provides quality assurance and reporting. Emmes has developed a number of routine reports specifically designed for monitors (e.g., listings of serious adverse events, etc.).

Additionally, Emmes has developed summary reports of discrepancies, as well as reports of the exceptions databases, which include requests and reasons for exceptions. The results of the reports are communicated back to site staff and along with protocol compliance issues, to the DSMC (if applicable).

Following the monitoring plan for this study, Emmes will perform monitoring activities, including on-site audits, review of database entries and the resolution of study issues. In addition to monitoring, Emmes performs various detailed automated and manual data quality checks. The results from these checks and any protocol compliance issues are communicated back to site staff and to the NEI Project Officer, NEI Clinical Director and applicable regulatory bodies.

